18.1 Product Compositions

		Impact Advanced Recovery ††	Oral Nutrition Control
Serving Size		6.0 fl oz	6.0 fl oz
Calories	kcal	200	185
Total Fat*	g	8	8
Sodium	mg	200	200
Potassium	mg	450	450
Total Carbohydrate	g	15	15
Total Sugars	g	~13	~13
Protein	g	18	14
Vitamin A**	IU	1126	1126
Vitamin C	mg	20	20
Calcium	mg	270	270
Iron	mg	4	4
Vitamin D	IU	152	152
Vitamin E	IU	14	14
Vitamin K	mcg	22	22
Thiamin	mg	0.4	0.4
Riboflavin	mg	0.6	0.6
Niacin	mg	5.3	5.3
Vitamin B6	mg	0.5	0.5
Folic Acid	mcg	65	65
Vitamin B12	mcg	0.8	0.8
Biotin	mcg	10	10
Pantothenic Acid	mg	2.7	2.7
Phosphorus	mg	240	240
Iodine	mcg	50	50
Magnesium	mg	75	75
Zinc	mg	5	5
Selenium	mcg	16	16
Copper	mg	0.3	0.3
Manganese	mg	0.7	0.7
Chromium	mcg	12	12
Molybdenum	mcg	15	15
Chloride	mg	400	400
Choline	mg	90	90

* Contains 1.3g MCT per 178 mL

**Includes 50% Vitamin A activity from Beta-Carotene

†† Includes 4.2 g of the amino acid L-arginine per 237 mL

18.2 Tertiary Objectives

- Frequencies of Myeloid-derived suppressor cells (MDSCs). Our team discovered that SIM restrains MDSC expansion. (1) Expansion of myeloid derived suppressor cells (MDSC) suppresses T-cells, and lowers the resistance to infection. Peripheral blood mononucleocytes (PBMCs) will be collected at baseline, post-operative Day 2 and post-operative Day 30 based on the findings of our pilot study. (2) Samples will be analyzed by flow cytometry as they are received at the University of Kansas. MDSC subpopulations are defined according to published methods of grouping granulocytic ((Lin- CD11b+ CD33+ CD14- CD15+), monocytic (Lin- CD11b+ CD33+ CD14+ CD15-), and immature (Lin- CD11b+ CD33+ CD14- CD15-). (3) [name] will run final analyses on all immune data.
- Neutrophil-to-lymphocyte ratio (NLR). NLR has been suggested as a biomarker for predicting clinical course in surgical populations. (4) In our pilot study, NLR was significantly lower in the SIM group compared to the ONS group 3 hours after incision ($P = 0.04$). (5) The complete blood count (CBC) with differential is taken as part of routine care. The ratio of the absolute neutrophil to lymphocyte count is obtained from this test. The lymphocyte count is also used to calculate the absolute number of MDSCs.
- Inflammation biomarkers related to complications and muscle wasting. Elevated IL-6 is associated with post-operative complications and muscle loss. Also, a depressed Th1 and dominant Th2 response after surgery is associated with infectious complications. In our pilot study, the change in plasma IL-6 levels from surgery to POD2 was significantly lower in the SIM group compared to the ONS group ($P = 0.022$), and the average IL-6 concentration in the plasma was significantly lower in SIM group compared to the ONS group on POD 2 ($P=0.020$), suggesting earlier resolution of inflammation in the SIM group. (6) SIM intake has reduced plasma IL-6 compared to control groups in other clinical trials. (7,8,9,10,11) Our pilot study also showed that Th1-Th2 balance was shifted towards Th1 three hours after incision, which may mean that participants were better able to ward off an infection. We measure Th1-Th2 balance by evaluating the ratios of IFNy:IL-4 and TNFa:IL-13. SIM intake has improved Th1-Th2 balance after colorectal surgery, which further supports our prediction. (12) Cytokines will be analyzed in our lab by MILLIPLEX MAP Human Th17 Panel, Magnetic, 8-plex with IL-6, IL-4, IFN gamma, IL-13, TNF alpha, IL-1b, IL-31, IL-5, and IL-17A run on all three blood draws (baseline, post-operative day 2, post-operative day 30) for each patient.
- Arginine deficiency & Plasma Amino Acid Metabolism. The systemic inflammatory response affects carbohydrate (glucose), lipid, and amino acid metabolism which all contribute to the adverse nutritional impact of cancer, surgical response, and infection. However, it is amino acid metabolism that is the final pathway responsible for lean tissue maintenance, loss, and repletion. Analyses of amino acid profiles are a critical piece to foster a better understanding of whether amino acid deficiencies persist even after SIM supplementation. These data are key to optimizing new nutrition interventions to help patients. Amino acid profiles provide insight regarding the dysregulated amino acid metabolism thought to play a role in how SIM supports the immune system, improves wound healing, prevents muscle degradation, and increases blood flow and tissue oxygenation. The theory surrounding the efficacy of SIM involves preventing arginine deficiency after surgery. (13) Our preliminary data revealed that prior to surgery, RC patients were arginine deficient. Sufficient levels of plasma arginine are based on the reference range, 80-100 μ mol/L. (14) However, SIM supplementation prevented further depletion of arginine at post-operative day 2, whereas arginine plummeted in the ONS group after surgery. Furthermore, our data

showed that the SIM group had significantly higher plasma ornithine concentrations compared to the ONS group at the time of surgery ($P = 0.001$) and ornithine concentrations were significantly different between the two groups over time ($P = 0.04$). Ornithine is the product of arginine metabolism by arginase, and these data suggest that the increase in ornithine reflects a greater availability of proline and polyamines, which contribute to better wound healing through collagen formation. Several ratios are available to help interpret the amino acid flux around trauma. A full panel of amino acids will be measured in the plasma using the Ultraperformance liquid chromatography (UPLC) with ultraviolet detection at the Institute for Metabolomic Disease, Baylor Research Institute. (15)

- **Nutrition Status.** We will screen and assess for malnutrition using the Patient-generated subjective global assessment (PG-SGA), version 2014, a validated tool for the oncology population which captures nutrition impact symptoms. (16) The PG-SGA will be completed by the patient and study team staff. A training video is available on the **S1600** study abstract page on the SWOG web site. The PG-SGA will be obtained at baseline to identify and categorize patients at risk for nutrition deficiency and will be repeated at the 30 day visit to monitor subjective short-term changes in nutritional status. The Scored PG-SGA includes patient-generated historical components (Weight History, Food Intake, & Nutrition Impact Symptoms) and a professional assessment (Diagnosis, Age, Metabolic stress, and Physical Exam). The malnutrition assessment will be used to categorize whether patients are: 1) well nourished, 2) moderately malnourished, or 3) severely malnourished. Change in grades of malnutrition at baseline and 30 days will also be evaluated. Nutrition status will be considered as a potential covariate as we analyze the data.
- **Background Dietary Intake.** On baseline and day 30, two 24-h dietary recalls (one weekday and closest weekend day) will be analyzed with Nutrition Data System for Research (NDSR). If the patient consents, his or her contact information will be obtained at registration. A study dietitian, staffed by [name], will interview the patient by phone at scheduled times. Dietary intake data gathered by interview is governed by a multiple-pass interview approach. (17) Five distinct passes provide multiple opportunities for the participant to recall food intake. The first pass involves obtaining from the participant a listing of all foods and beverages consumed in the previous 24 h. This listing is reviewed with the participant for completeness and correctness (second pass). The interviewer then collects detailed information about each reported food and beverage, including the amount consumed and method of preparation (third pass). In the fourth pass, the interviewer then probes for commonly forgotten foods. Finally, the detailed information is reviewed for completeness and correctness (fifth pass). Energy, macronutrients, fish oil, arginine, EPA, DHA, vitamin A, and dietary supplement intake will be summarized and reported to control for the background diet. Background diet will be summarized and reported to control for the background diet.
- **Measures of Treatment Compliance Biomarkers.** Plasma fatty acid profiles are biomarkers of intake compliance enhancing the rigor of our study. The high concentrations of EPA and DHA in the formula will be reflected in the plasma phospholipid fatty acid composition as demonstrated by Senkal et al. Plasma fatty acid profiles reflect fat intake over the previous days to weeks and triacylglycerides reflect fat intake over the previous hours to days making these ideal compliance markers for our intervention. Plasma fatty acid profiles will be analyzed by gas chromatography and reported as weight percent of total fatty acids. The fatty acid profiles from the day 2 post-surgery blood will be measured by collaborator [name].

- **Neutrophil Extracellular Traps (NETs).** NETs are meshes of DNA with associated neutrophil enzymes, including proteases such as Neutrophil Elastase and myeloperoxidase. NETs are detected in plasma from humans and mice with lung inflammation using a sandwich enzyme-linked immunosorbent assay (ELISA). The amount of NETs is determined by a sandwich ELISA using antibodies against the DNA scaffold and the NET-associated protease neutrophil elastase. ABTS is used as a substrate for the HRP (HorseRadish Peroxidase) conjugated Anti-DNA antibody and given an absorbance reading value (at 405 nm) used to compare the samples. 50 microliters of plasma are needed to perform this assay (150 microliter would be the best to be on the safe side and to perform duplicates). In this assay, developed by the [name] lab, healthy donors have no detectable NETs while transfusion related acute lung injury (TRALI) patients have values of \approx 200-times that of healthy donors. The NETs will be measured at baseline, post-operative Day 2 and post-operative Day 30 by collaborator [name].

Tertiary objectives include comparing the impact of consuming SIM compared to ONS for restraining MDSCs, decreasing inflammation, and modulating nutrient metabolism. To limit the influence of outliers and aid interpretation across a panel of markers, the marker level results will be log normal-standardized and split at the median level, creating an indicator variable (high vs. low levels of each marker). Assuming complete information, the accrual goal of $n = 200$ total patients will provide adequate power ($>80\%$) to detect a $>20\%$ change in the proportion of patients with high or low marker levels due to SIM, based on a two-arm normal design, one-sided alpha = 0.05 testing, and assuming the average rate of high or low marker levels across arms of 50%.

In addition, we will examine whether these biomarkers influence the association between intervention and the clinical outcomes. As a more exploratory analysis, we will use a two-sided nominal P -value = 0.10 to identify potentially significant interactions. (18) Under a binomial interaction design, equal sample sizes in each cell, a one-sided alpha = 0.10, and a 65% event probability for the ONS arm, $n = 200$ patients will give adequate power ($\geq 80\%$) to detect a 3.8-fold increased odds of complications on the ONS arm in stratum 1 (i.e., high-expression group) if there is no effect in stratum 2 (i.e., low-expression group). In the case of a significant interaction indicating differential complication rates by arm between marker categories, further specific analyses will be performed to identify the actual differences. It is recognized that these results will not be definitive due to the limited power and multiple testing problem, although hypotheses will be based on biologic rationale. Promising observations will need to be validated in future data sets due to the exploratory nature of this component of the study.

We will also explore whether dietary intake variables, derived from data obtained from the dietary intake telephone interview, influence the association between intervention and outcome. The specific variables of interest include calorie intake, protein intake, nutrition status, and immune-enhancing nutrients.

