1.3 Tertiary Objectives

- a. To assess the impact of SIM use on the expansion of myeloid-derived suppressor cells.
- b. To assess the impact of SIM use on pro-inflammatory cytokines and neutrophil: lymphocyte ratios.
- c. To assess the impact of SIM use on post-operative arginine deficiency and amino acid metabolism.
- d. To explore the association of dietary intake variables (nutrition status, calories, protein, and immune-enhancing factors) and study outcomes.

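### The plan asks whether arginine deficiency persists on SIM, but no planned analysis estimates the proportion of patients who are deficient

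*Combined protocol and SAP*

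**What the plan says.** Section 1.3, objective c, reads: "To assess the impact of SIM use on post-operative arginine deficiency and amino acid metabolism".

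The arginine item in section 18.2 sets an absolute standard: "Sufficient levels of plasma arginine are based on the reference range, 80-100" (umol/L). It reports the pilot starting point, "Our preliminary data revealed that prior to surgery, RC patients were arginine deficient", and says the amino acid profiles are needed to learn "whether amino acid deficiencies persist even after SIM supplementation".

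The statistical text later in 18.2 covers the tertiary comparisons of SIM with ONS together, namely "restraining MDSCs, decreasing inflammation, and modulating nutrient metabolism". Its rule for the markers is: "the marker level results will be log normal-standardized and split at the median level", "creating an indicator variable (high vs. low levels of each marker"). The accompanying power statement uses 200 patients with complete information, a change of more than 20% in the high or low share, and "one-sided alpha = 0.05 testing, and assuming the average rate of high or low marker levels across arms of 50" percent.

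The same section also plans multivariable logistic regression, means and standard deviations of marker levels by time point, examination at Day 2 and Day 30, and linear mixed models over baseline, Day 2 and Day 30. The 80-100 range appears in none of these.

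**The concern.** Deficiency is a statement about an absolute level; high or low at the median is a statement about rank within the trial. If the median is taken over both arms, half of all patients are high whatever the arginine level. If most patients sit below 80 umol/L, as the pilot remark about the pre-surgery state suggests they might, the median is also below 80 and many patients labelled high are deficient.

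What is at stake is interpretation. A significant rise in the high share on SIM could be reported as deficiency prevented or corrected when the analysis cannot show that. The trial would also lack a pre-specified estimate for the persistence question that 18.2 itself poses.

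**Working it through.** **1. The plan's own power figure.** Inputs from 18.2: 200 patients, one-sided alpha 0.05, average rate 50%, change above 20%. Assumed: 1:1 allocation (100 per arm) and 20% read as percentage points, so 60% versus 40%.

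Power = Phi{[d - 1.645 x sqrt(2 x pbar x (1 - pbar)/n)] / sqrt[(p1(1 - p1) + p2(1 - p2))/n]}

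= Phi{[0.20 - 1.645 x sqrt(0.50/100)] / sqrt(0.48/100)} = Phi(1.21) = 88.6%.

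The stated power above 80% reproduces. Read as a relative change (55% versus 45%), power would be 40.8%, so the absolute reading is the one that fits. A 50% average across arms is what a median pooled over both arms produces; the text says only that the split is at the median, so the pooled reading is an inference.

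**2. What the split shows and what it leaves open.** The documents give no arginine mean, SD or deficiency rate, so every value below is assumed. Arginine is taken as normal with equal SD in two equal arms, so the pooled median c is the midpoint of the two means. Then P(high) = 1 - Phi[(c - mean)/SD] and P(80 or above) = 1 - Phi[(80 - mean)/SD].

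| Assumed mean ONS / SIM, SD (umol/L) | c | High, ONS vs SIM | 80 or above, ONS vs SIM | Below 80 on SIM |
|---|---|---|---|---|
| 40 / 55, 15 | 47.5 | 31% vs 69% | 0.4% vs 4.8% | 95% |
| 50 / 65, 20 | 57.5 | 35% vs 65% | 7% vs 23% | 77% |
| 60 / 75, 20 | 67.5 | 35% vs 65% | 16% vs 40% | 60% |

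Example, second row, SIM: P(high) = 1 - Phi[(57.5 - 65)/20] = 1 - Phi(-0.375) = 65%; P(80 or above) = 1 - Phi[(80 - 65)/20] = 1 - Phi(0.75) = 23%.

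The second and third rows give the same median-split result but different deficiency rates. Lognormal arms with log SD 0.25 widen the range. Medians of 45 and 55 give 34% versus 66% high with 98.9% versus 93.3% below 80. Medians of 75 and 90 give 36% versus 64% high with 60% versus 32% below 80.

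**3. What a cut at 80 would cost in power** (100 per arm, one-sided 0.05).

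- First row (0.4% vs 4.8%): about 0.4 + 4.8 = 5 patients in the whole trial reach 80. Power is about 41% by Fisher's exact test (62% by the formula in step 1), against more than 99.9% for the median split.
- Second and third rows: about 93% and 98% by Fisher's exact test.
- A 20-point fall in the deficient share (formula in step 1): 99.2% for 95% to 75%, 97.5% for 90% to 70%, 93.0% for 80% to 60%, 89.8% for 70% to 50%.

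A cut at 80 is therefore adequate in much of the assumed range and weak where almost nobody reaches 80.

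**The case against.** The other side has four good arguments.

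- The arms are free to differ under a pooled-median split; only the combined share is fixed at 50%. As a comparison of relative arginine level it is valid, and 18.2 gives reasons for it (limiting outliers, a common scale across a panel). This stands.
- The planned means, SDs and mixed models inform the question. A mean of 55 with SD 15, set beside the 80-100 range, would already suggest that deficiency persists. This stands in part: the text does not say that the descriptive summaries are by arm or that the raw scale is kept, and neither analysis yields a proportion deficient.
- The pilot effect is relative: SIM prevented further depletion while levels in the ONS group dropped steeply. A cut at 80 could miss a difference between two levels that are both below 80. This stands, and step 3 shows the loss in the first row. It is a reason to add the cut, not to substitute it.
- The marker is tertiary, and the percentage below 80 could be tabulated later from the assay values. True, but a cut fixed in advance avoids a post hoc choice.

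A reader might infer that the median split invalidates the arginine comparison, that the trial can learn nothing about deficiency, or that the split should be replaced by the cut at 80. The documents support none of these, for the reasons above. Nor do they establish that the Day 2 median will lie below 80: the pilot remark concerns the pre-surgery state, and one arm is supplemented.

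**Conclusion.** The gap between question and analysis is real. The plan asks about deficiency and its persistence and states a sufficient range, but never estimates or compares the proportion outside it. A difference in the high share supports a statement about relative arginine level only. Under the assumed values, one and the same median-split result (35% versus 65%) is compatible with 77% or with 60% of SIM patients still below 80.

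This rests on three readings: that the median is the trial's pooled median (inferred from the 50% average), that arginine falls under the common marker rule (nutrient metabolism is named in the same paragraph), and that below 80 umol/L counts as deficient (the lower end of the stated sufficient range). All magnitudes are illustrations. The consequence is confined to a tertiary objective; it is a cheap improvement, not a threat to the primary or secondary conclusions.

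**What to change.** In section 18.2, keep the median split and the continuous mixed model for arginine, and add:

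- the number and percentage of patients below 80 umol/L by arm at Day 2 and at Day 30, with a between-arm difference and confidence interval;
- adjustment for the stratification factors and baseline arginine where event counts allow, and an exact unadjusted comparison otherwise;
- a statement that only this result supports a claim about arginine deficiency, and that the median split supports a claim about relative level.

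The cost is a few sentences and one extra tertiary analysis, using the same samples, the same assay and a limit already in the protocol. The downside is imprecision if very few patients reach 80, as in the first row of the table, where about five patients in the trial would do so. The percentages would still describe whether deficiency persists, and the mixed model would stand beside them.

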11.0 STATISTICAL CONSIDERATIONS

11.1 Primary Analysis

The primary objective is to compare, by arm, the proportion of patients who experience any complication (Clavien-Dindo grades I–V) by day 30 after surgery. Prior evidence suggests that approximately 65% of patients will experience complications by Day 30. (120, 121, 122, 123) The design stipulates that a 35% relative reduction in the complication rate due to the intervention would be clinically meaningful, representing a reduction in the complication rate from 65% down to 42% (a 23% absolute reduction). The design also anticipates a 5% non-adherence rate (which reduces the nominal effect size). Based on a two-arm binomial design with continuity correction, a one-sided alpha = 0.05 test and 80% power, a total of 146 eligible, randomized patients will be needed. In addition, in this population, it is anticipated that 20% of patients will drop out after surgery by Day 30, and a small portion of patients (3%) will drop out prior to surgery. Incorporation of this dropout rate inflates the required sample size by a factor of $146/0.77 = 190$ eligible patients. Finally, assuming a 5% ineligibility rate, a total of 200 registered patients will be required. The high-grade complication rate (Clavien Dindo scheme III–V) will also be examined. If the control arm high grade complication rate is 20%, 200 patients will give $\geq 80\%$ power to detect an absolute reduction of 15% (down to 5%).

The primary analysis will be based on a multivariable logistic regression under intent-to-treat among all randomized patients, irrespective of their eligibility status, adjusting for the specified stratification factors: a. Diversion type (neobladder vs. ileal conduit); b. Prior neoadjuvant chemotherapy (any vs. none); and c. Nutrition status (well-nourished vs. moderate malnutrition). A Fisher's exact test will also be conducted to establish whether the results are sensitive to model assumptions. A single interim analysis for efficacy will be conducted when 50% of patients achieve their endpoint at the alpha=0.005 level. Accordingly, the final analysis will be conducted at the alpha=0.045 level. A separate analysis among all eligible randomized patients will also be conducted.

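### The biomarker-by-arm interaction will be tested two-sided at 0.10 but was powered one-sided at 0.10, so the stated power of at least 80% is about 72%, and about 61% in the patients expected to be evaluable

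*Combined protocol and SAP*

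**What the plan says.** Section 18.2 (Tertiary Objectives) dichotomises each marker at its median and asks whether the marker modifies the effect of the intervention on clinical outcomes. The decision rule is: "we will use a two-sided nominal P -value = 0.10 to identify potentially significant interactions".

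The power sentence follows directly. It assumes "equal sample sizes in each cell, a one-sided alpha = 0.10, and a 65% event probability for the ONS arm". It claims at least 80% power with 200 patients to detect a "3.8-fold increased odds of complications on the ONS arm in stratum 1", "if there is no effect in stratum 2". The same paragraph then says the results will not be definitive because of limited power and multiple testing.

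On numbers, Section 11.1 (Primary Analysis) says "it is anticipated that 20% of patients will drop out after surgery by Day 30". It adds 3% dropout before surgery and 5% ineligibility. These rates take the 200 registered patients down to the 146 on which the primary comparison is sized.

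**The concern.** The power figure and the decision rule belong to different tests. A one-sided 0.10 test rejects beyond 1.282 standard errors, whereas a two-sided 0.10 test needs 1.645. Nothing in the text links the two or explains the change.

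The sample size is a second, separate problem. The outcome in the power sentence is complications, with the same 65% control rate as the Day 30 primary endpoint. The calculation counts every registered patient, including those the protocol expects to lose before that outcome is known.

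The marker work is meant to explain mechanism, and the Background says even a negative trial could inform disease biology. A null interaction will be judged against the stated power. If that power is too high, a null result looks more informative than it is.

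**Working it through.** **Inputs**

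- Test as planned: two-sided 0.10, critical z = 1.645 (Section 18.2).
- Test as powered: one-sided 0.10, critical z = 1.282 (Section 18.2).
- Four equal cells, arm by marker stratum (Section 18.2): 200/4 = 50 per cell.
- Complication rate on the control drink (ONS): 0.65 in both strata (Section 18.2).
- Stratum 2: no effect, so the rate on the immune-modulating drink (SIM) is also 0.65.
- Stratum 1: odds ratio 3.8. SIM odds = (0.65/0.35)/3.8 = 1.857/3.8 = 0.489, so the SIM rate is 0.489/1.489 = 0.328.
- Expected evaluable: 200 × 0.95 × 0.77 = 146.3, that is 146, or 36.5 per cell (Section 11.1).

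**Formula**

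The protocol names a binomial interaction design without giving a formula. I used a Wald test of the difference in log odds ratios, which is the scale of the logistic regression planned in Section 18.2:

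SE² = Σ 1/[n p(1 − p)] over the four cells; power = Φ(ln 3.8 / SE − z).

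**Reproducing the stated figure (200 patients, one-sided 0.10)**

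- SE² = 3/(50 × 0.65 × 0.35) + 1/(50 × 0.328 × 0.672) = 0.2637 + 0.0907 = 0.3544, so SE = 0.595.
- ln 3.8 = 1.335, and 1.335/0.595 = 2.242.
- Power = Φ(2.242 − 1.282) = Φ(0.961) = 83.2%. This agrees with the claim of at least 80%.

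**The planned test (200 patients, two-sided 0.10)**

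- Power = Φ(2.242 − 1.645) = Φ(0.597) = 72.5%.

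**With 146 evaluable**

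- SE = 0.595 × √(50/36.5) = 0.697, and 1.335/0.697 = 1.916.
- One-sided: Φ(1.916 − 1.282) = 73.7%. Two-sided: Φ(1.916 − 1.645) = 60.7%.

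| Patients | One-sided 0.10 | Two-sided 0.10 | Odds ratio for 80% power, two-sided |
|---|---|---|---|
| 200 | 83.2% | 72.5% | about 4.4 |
| 146 | 73.7% | 60.7% | about 5.9 |

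To keep 80% power for an odds ratio of 3.8 with the two-sided test, z must be 1.645 + 0.842 = 2.486. That needs 200 × (2.486/2.242)² ≈ 246 evaluable patients.

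**Sensitivity to method**

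- Other null-variance forms give 72.7% to 74.7% two-sided at 200.
- Simulating the Wald test (200,000 runs) gives 83.4% to 83.7% one-sided and 73.2% to 73.7% two-sided at 200. At 146, the two-sided result is 60.3% to 61.4%.
- On the risk-difference scale, two-sided power is 77.3% at 200 and 65.6% at 146.
- If 65% is instead the SIM rate in stratum 1 and the ONS odds are raised 3.8-fold, power at 200 is 76.2% to 80.5% one-sided and 63.7% to 70.5% two-sided. This reading fits the text less well.

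No variant brings the two-sided test at 200 patients to 80%.

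**The case against.** The strongest objection concerns impact. The analysis is tertiary, is labelled exploratory, and carries its own warning about limited power and the need for validation. No sample size, stopping rule, or primary or secondary inference depends on it. That stands and keeps the matter small. It does not correct the figure, because the same paragraph describes the power as adequate and puts a number on it.

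Second, 61% is not due to sidedness alone. Losing patients, with the one-sided test kept, already lowers power to 73.7%. That is correct, and the two causes should be kept apart. The preceding power statement, on marker proportions, is conditional on complete data, and one could argue that the same convention carries over. The interaction sentence does not say so, and Section 18.9 sizes the microbiome work on 146.

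Third, 146 excludes ineligible patients, whereas the primary analysis keeps them. On that basis the number is 200 × 0.77 = 154 and two-sided power is 62.7%, a difference of 2 points. No population is named for the interaction analysis.

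Fourth, the method is unstated, so exact percentages depend on a choice. Even the most favourable scale tried stays below 80%, and the planned logistic regression makes the log-odds scale the natural one.

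Finally, the authors may have intended a one-sided test, as in their other arm-comparison power statements. Then the decision rule is the sentence to change. The two sentences still conflict, and the use of 200 remains.

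**Conclusion.** The concern holds. The stated power of at least 80% belongs to a one-sided 0.10 test. For the two-sided 0.10 test that the protocol prescribes, power for a 3.8-fold odds difference is about 72% with 200 patients (up to 77% on a risk-difference scale). It is about 61% with the 146 expected to be evaluable, or 63% with 154. The chance of missing the stated effect is therefore about 27% to 39%, rather than at most 20%.

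These figures assume equal cells, a 65% complication rate in the three cells without effect, and no covariate adjustment. They do not allow for missing marker samples, or for unequal cells if SIM shifts post-baseline markers. Either would reduce power further. Because the analysis is exploratory, this is a correction that should be made but does not threaten the trial's main conclusions.

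**What to change.** Use one sidedness for the test and its power. Keeping the two-sided 0.10 rule, the power sentence should say: about 72% power for a 3.8-fold odds difference with 200 patients, and 80% for about 4.4-fold; with 146 evaluable, about 61% and about 5.9-fold. The sponsor should confirm these with its own method and name the analysis population. If a one-sided test was intended, the decision rule should be changed before the data are analysed and the direction of the interaction stated; power is then about 83% at 200 but 74% at 146.

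The cost is rewording one or two sentences and accepting a less favourable figure. Enrolment, data collection and patient care do not change.
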